11.3.1 Suspected Adverse Drug Reactions (ADRs)

An additional summary of suspected ADRs as specified in CSL112 investigator brochure (Version V12, Section 7.5, Table 35) will be provided, sorted in descending order of frequency by PT in the CSL112 arm. PTs related to the following categories of adverse events are defined consistent with the current CSL112 investigator brochure.

- Injection and infusion site reactions
- Venipuncture and catheter site related reactions
- PTs corresponding to high level term of Headaches NEC
- PTs corresponding to high level term of Urinary Tract Infection
- Single PT of Myalgia

Supportive listings of adverse events meeting definitions of suspected ADRs will be provided.

11.3.2 Summary of Infusion Site or Injection Site Reactions

Local tolerability reactions will be analyzed based on groupings of PTs. Infusion and injection site reactions, and venipuncture and catheter site reactions had been identified as ADRs in the completed CSL112 clinical studies. A table will be provided for each grouping of terms below, which will be summarized by PT and treatment group:

- Infusion site reactions: all PTs beginning with “infusion site”
- Injection site reactions: all PTs beginning with “injection site”
- Venipuncture and catheter site reactions: all PTs beginning with “catheter site”, “puncture site”, “vascular site access”, “vessel puncture site”.

The summary table will be sorted in descending order by frequency of PT in the CSL112 arm.

11.4 Public Disclosure of Clinical Trials Requirements

To support public disclosure requirements for a clinical study, a summary of SAEs and their relationship to study treatment will be provided. These summaries will be displayed by SOC and PT and will include number and percentage of subjects for each SAE and the number of instances of each.

Additionally, a summary of only non-serious TEAEs occurring in at least 5% of the subjects in at least one treatment arm will be provided. The summary will be displayed by SOC and PT and will include number and percentage of subjects for each TEAE and the number of instances of each TEAE. It will be sorted in decreasing frequency of incidence in the CSL112 arm.

Summaries to be produced are:

- Treatment-emergent SAEs by SOC and PT
- Treatment-emergent SAEs by SOC and PT with Relationship to Study Treatment
- Non-Serious AEs experienced by more than 5% of subjects in any treatment group, by SOC and PT
- Non-Serious AEs by SOC and PT.

11.5 Pregnancies

While pregnancy itself is not considered to be an AE or SAE, any pregnancy complication or elective termination of a pregnancy for medical reasons will be recorded as an AE or SAE as described in the protocol. If a subject or a subject's partner becomes pregnant while on the study, the information will be included in the narratives and no separate table or listing will be produced.

11.6 Clinical Laboratory Evaluations

11.6.1 General Considerations for Laboratory Data

The list of planned laboratory parameters to be evaluated in this study is shown in Table 11-1.

Table 11-1 List of Planned Laboratory Parameters

Hematology	Hemoglobin	Hematocrit	WBC counts
	Total platelet count	CBC with differential	
Biochemistry	Alkaline phosphatase	ALT	AST
	TBili	Direct bilirubin	BUN
	Cholesterol ^a	LDL cholesterol ^a	HDL cholesterol ^a
	Creatinine	eGFR (calculated)	Triglycerides ^a
	Indirect bilirubin (calculated)		

- ALT = alanine aminotransferase; AST = aspartate aminotransferase; BUN = blood urea nitrogen; eGFR = estimated glomerular filtration rate; cholesterol = total cholesterol; LDL = low density lipoprotein; HDL = high density lipoprotein; CBC = complete blood count; ALT = alanineaminotransferase; AST = Aspartate aminotransferase.
- ^a Lipid panel test results will remain blinded

With the exception of ALT and Tbili used to identify potential hepatic injury events, analysis of clinical laboratory data will be based on results from the central laboratory. Local laboratory results will be included in data listings. The definition of baseline value given in [Section 8.2.5](#) will be applied when assessing change from baseline. The denominator in calculating any percentage will be the number of subjects with a non-missing, valid result at that time point; for shift tables, the denominator corresponds to the number of subjects with a valid result at both baseline and study visit of interest. The laboratory normal reference ranges will be provided and clinical laboratory test results outside the normal reference range will be flagged in the laboratory data listings.

When quantitative laboratory measurements reported are with qualifiers such as “< lower limit of normal” or “> upper limit of normal”, the numeric portion of the laboratory result will be used for the purpose of summarizing the data; however, the actual result will be presented in data listings.

Quantitative laboratory measurements will be categorized based on a comparison with the relevant reference normal range (SI units) as follows:

- Low: Below the lower limit of the normal range
- Normal: Within the normal range
- High: Above the upper limit of the normal range

11.6.2 Analysis of Clinical Laboratory Data

The laboratory data will be summarized as described below for all parameters:

- Actual and change from baseline will be presented by scheduled study visit for quantitative values. Unscheduled assessments will be excluded.
- Analysis of shifts from baseline to worst observation will be summarized. For hemoglobin, hematocrit, and platelets, ‘Low’ values will be considered in determining the worst observation whereas ‘High’ values will be of interest for laboratory parameters including WBC, alkaline phosphatase, ALT, AST, and bilirubin (total, direct, and indirect). Worst value determination will include scheduled and unscheduled assessments.
- Box plots of actual values and change from baseline will be presented by treatment and study visit
- The number (%) of subjects meeting the grade 3 or 4 toxicity criteria [CTCAE] for select renal and hepatic parameters as defined in [Table 11-2](#) will be summarized.

Table 11-2 Select Renal and Hepatic Grades 3 and 4 Laboratory Abnormalities

Lab parameter	Grade 3	Grade 4
Alkaline phosphatase	> 5 - 20x ULN	> 20x ULN
ALT	> 5 - 20x ULN	> 20x ULN
AST	> 5 - 20x ULN	> 20x ULN
TBili	> 3x - 10x ULN	> 10x ULN
Direct bilirubin	> 3x - 10x ULN	> 10x ULN
Indirect bilirubin	> 3x - 10x ULN	> 10x ULN
Creatinine	> 3x Baseline > 3 - 6x ULN	> 6x ULN

11.6.2.1 Renal Function:

Additional summaries of serum creatinine and eGFR (for derivation, see [Table 8-1](#)) will be presented to characterize the effect of CSL112 on renal function. The tables listed below will be generated for all subjects as well by subgroups defined on the basis of renal function categories and by time delay between contrast administration and IP administration, both alone and in combination. The three renal function subgroups are defined as normal (eGFR ≥ 90 mL/min/1.73 m²), mild renal impairment (eGFR ≥ 60 to < 90 mL/min/1.73 m²), and moderate renal impairment (eGFR ≥ 30 to < 60 mL/min/1.73 m²). The three subgroups for time delay between administration of contrast and IP are defined as < 24 hours, ≥ 24 hours- < 48 hours and ≥ 48 hours. Thus, there are a total of nine subgroups:

- Categories of absolute change from baseline in serum creatinine defined as \leq baseline value, > 0 to < 27 , ≥ 27 to ≤ 44 , > 44 μ mol/L (> 0 to < 0.3 , ≥ 0.3 to ≤ 0.5 , and > 0.5 mg/dL); number (%) of subjects in each category will be presented. Categorization of change from baseline in serum creatinine will be based SI units (μ mol/L) while conventional units are given for descriptive purposes.
- Number (%) of subjects achieving a threshold rise of ≥ 27 μ mol/L (0.3 mg/dL) one or more occasions as well as on two or more consecutive occasions will be presented
- Categories of increase in serum creatinine including $\geq 1.5 \times$ baseline, $\geq 2 \times$ baseline, $\geq 3 \times$ baseline

- Number (%) of subjects with raw serum creatinine value $\geq 354 \mu\text{mol/L}$ (4.0 mg/dL)
- Decreases in eGFR of 25% or more from baseline at any time
- Supportive data listings of individual subject data meeting the above-mentioned criteria will be generated
- Data listings including subjects with one or more values outside the reference range will be produced

Assessment of Drug-Biologic Interactions:

Incidence of elevations in serum creatinine defined as a change from baseline $\geq 27 \mu\text{mol/L}$ (0.3 mg/dL) will be summarized by concomitant use of ACEI or ARBs where concomitant is defined for this summary as any time during the active treatment period.

11.6.2.2 Hepatic function:

Liver Dysfunction:

The number (%) of subjects experiencing concomitant elevations in ALT $> 3 \times \text{ULN}$ and Tbili $> 2 \times \text{ULN}$ or ALT $> 5 \times \text{ULN}$ will be determined. Incidence rates along with 95% CI s [Newcombe, 1998] will be provided. A plot of TBili versus ALT will be generated.

Assessment of Drug-Biologic Interaction:

The impact on liver function due to potential interactions between CSL112 and statins and PCS K9 inhibitors will be investigated by summarizing the incidence of elevations (ALT $> 3 \times \text{ULN}$ and Tbili $> 2 \times \text{ULN}$ or ALT $> 5 \times \text{ULN}$) in ALT and TBili in the following subgroups:

- No statins and no PCSK9i
- No statins and any PCSK9i
- Low or moderate potency statins and no PCSK9i
- Low or moderate potency statins and any PCSK9i
- High potency statins and no PCSK9i
- High potency statins and any PCSK9i

11.7 Other Safety Measures

11.7.1 Evaluation of Immunogenic Potential

Of the subjects with blood samples assayed for anti-drug antibodies (ADA), the number (%) of subjects positive for binding antibodies to CSL112 and apoA-I will be summarized.

Immunogenicity results for routine samples will be separately summarized from those samples taken to assess hypersensitivity reactions.

11.7.2 Vital Signs

The following Vital Signs measurements will be reported for this study:

- Systolic Blood Pressure (SBP) (mmHg)
- Diastolic Blood Pressure (DBP) (mmHg)
- Pulse (bpm)
- Weight (kg)

The following summaries will be provided:

- Actual and change from baseline by visit
- Incidence of treatment emergent markedly abnormal vital signs will be derived according to the rules defined in [Table 8-2](#).

If a subject has a shift from baseline to both low and high, then the subject will be counted in both the low and the high categories.

- Incidence of subjects meeting markedly abnormal values
- Listing of all Vital Signs data and of subjects meeting markedly abnormal criteria
- For SBP, DBP and pulse, the change from baseline at each visit and by treatment group will be presented visually using box plots.

11.7.3 Physical Examination

A brief, directed physical examination focusing on pulmonary and CV exam, will be performed at screening and any clinically significant changes occurring between screening and Visit 8/Day 90, including drug hypersensitivity findings will be documented in the eCRF as an AE. Accordingly, no summary tables or listings will be produced.

11.7.4 Parvovirus Testing

Samples will be collected from all randomized subjects at Visit 2 (Day 1; before infusion 1) and Visit 6 (Day 29). Nucleic acid testing and serology (parvovirus B19) will be performed using complete samples (at Day 1 and 29) from approximately 300 randomly selected subjects (approximately 150 CSL112 and 150 placebo) to evaluate changes from baseline (ie, evidence of seroconversion or infection) for parvovirus B19.

Central lab results for Parvo 19 antibodies IgG and IgM will be categorized as negative, equivocal, or positive. Parvo B19 DNA will be reported as detected/not detected. A shift analysis of change from baseline to Visit 6 will be presented.

A subject data listing including central laboratory results for human parvovirus B19, Parvovirus B19 IgG antibody and Parvovirus B19 IgM antibody will be provided.

12 PK Analyses

PK sub-study will be performed to conduct a population PK analysis. Accordingly, blood samples will be drawn at pre-infusion 1, end of infusion 1, and end of infusion 4. The concentrations of apoA-I and PC will be assayed. The following PK endpoints are planned:

- Baseline-corrected apoA-I concentrations [concentration at end of infusion 1 or 4 minus baseline]
- Baseline-corrected plasma PC concentrations [concentration at end of infusion 1 or 4 minus baseline]
- Concentration in plasma at the end of infusion for apoA-I and PC
- Accumulation ratio for apoA-I and PC [Baseline corrected concentration at end of infusion 4 / baseline corrected concentration at end of infusion 1]

Plasma concentrations of apoA-I and PC will be assayed from the blood samples drawn in the planned PK sub-study. Plasma concentrations will be descriptively summarized by treatment and nominal sampling time points. Geometric mean ratios of apoA-I at the end of infusions 1 and 4 relative to baseline will be summarized. In addition, a population PK analysis will be conducted to further characterize the relationship between the plasma concentrations of apoA-I and demographic and baseline characteristics, that will be reported separately.

13 PD Analyses

The following pharmacodynamic endpoints are included to support the exploratory objective assessed in the PD sub-study:

- a. Total cholesterol efflux
- b. ABCA1-dependent efflux
- c. ABCA1-independent efflux

15.1 Description of Win Ratio Methodology

The unmatched win ratio method [Pocock et al, 2012] is employed to analyze the composite endpoint of recurrent hospitalizations for coronary, cerebral, or peripheral ischemia or all-cause death over 90 days by allowing for clinical priorities; ie, that death is a more important outcome than hospitalization.

In the unmatched win ratio approach, every subject on CSL112 is compared with every subject on placebo, each time noting who ‘won’. If N_t and N_c are the total number of subjects assigned to CSL112 (test treatment) and placebo (control treatment) then a total of $N_t \times N_c$ paired comparisons are made. Each pair is classified into one of five categories (a), (b), (c), (d), or (e) as shown below:

- a. CSL112 subject experienced death first [CSL112 loser]
- b. Placebo subject experienced death first [CSL112 winner]
- c. CSL112 had a greater number of hospitalizations [CSL112 loser]
- d. Placebo subject had a greater number of hospitalizations [CSL112 winner]
- e. None of the above (a tie)

For each pair, CSL112 is a ‘winner’ or ‘loser’ according to which subject experienced death first. If no death occurred by Day 90, then whether CSL112 is labelled a ‘winner’ or ‘loser’ depends on which subject had more hospitalizations. Otherwise, the two treatments are tied. The number of matched pairs in categories a, b, c, d, and e are summarized by N_a , N_b , N_c , N_d , and N_e , respectively. The number of winners and losers on CSL112 are defined as $N_w = N_b + N_d$ and $N_L = N_a + N_c$ with $Rw = N_w / N_L$ defined as the win ratio.

The derivation of a 1-sided P value for the win ratio is given below:

Let total sample size, $N = N_t + N_c$

For each paired comparison ij where Treatment for subject i is not equal to Treatment for subject j, let $U_{ij} = +1$, -1 , or 0 according to whether patient i is the winner, loser or they tied. Then for patient i, define $U_i = \sum U_{ij}$ where U_i is a positive integer if patient i wins more than loses. Further define $T = \sum U_i D_i$ where $D_i = 1$ if patient i is assigned to CSL112 and 0

otherwise. The variance of T is given by V where $V = \left(\frac{N_t N_c}{N(N-1)} * \sum U_i^2 \right)$ under the null hypothesis of no true difference between CSL112 and placebo. Then $z = \frac{T}{\sqrt{V}}$ is a standardized normal deviate, and the one-sided p-value is obtained from a cumulative normal distribution as $1 - \text{prob}(Z \leq z)$. Corresponding SAS code is given as $1 - \text{CDF}('NORMAL', z)$.

A win ratio (CSL112: Placebo) > 1 is indicative of superiority of treatment with CSL112 over placebo.

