**Apolipoprotein A-I**

---

ratio (CSL112: Placebo) and its 2-sided 95% confidence interval will be estimated from the model. A cumulative plot of recurrent hospitalization events will be generated.

A sensitivity analysis of the hospitalization data will be performed to explicitly incorporate death into the outcome using the Win Ratio [Pocock et al, 2012] method. This approach recognizes clinical hierarchies within composite outcomes. With the planned endpoint, death will be weighted more heavily relative to the total number of CV hospitalizations during 90 days from the time of randomization. The unmatched win ratio (CSL112: Placebo) will be calculated along with associated 2-sided 95% CI and a 1-sided *P* value. A complete description of the analytical approach will be provided in the SAP.

In addition, hospitalizations per thousand subject-years will be summarized by treatment group for descriptive purposes.

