In addition, for descriptive purposes, hospitalizations per thousand subject-years of follow-up will be summarized by treatment group.

The leading analysis of the hospitalizations endpoint described above is focused on the estimation of a rate ratio (CSL112: placebo) to determine whether treatment with CSL112 reduces the mean number of hospitalizations during the 90 day period. This approach accounts for death indirectly by adjusting the mean incidence for the duration of exposure but otherwise ignores death in the analysis. Thus, it provides a pharmacoeconomic assessment of treatment benefit afforded by CSL112.

A sensitivity analysis of the hospitalization data will be performed to explicitly incorporate death into the outcome using the Win Ratio [[Pocock et al, 2012](#)] method. This approach recognizes clinical hierarchies within composite outcomes. With the planned endpoint, death will be weighted more heavily relative to the total number of CV hospitalizations during 90 days from the time of randomization. The Win Ratio (CSL112: Placebo) will be calculated along with associated 95% CI and a 1-sided P value. A complete description of the analytical approach is given in [Appendix 15.1](#).

10.2.2 Time to first occurrence of CV Death, MI, or stroke from the time of randomization through 180 days

The derivation of time to first occurrence of CV Death, MI, or stroke from the time of randomization through 180 days is given below. The analytical details are similar to that described for the primary efficacy endpoint and hence a general description is given here.

	Time to Event (days) [TTE]	Censoring Status [Censor]
First of positively adjudicated CV Death, MI, or stroke during the 180 days following randomization	(date of MACE – randomization date) + 1	0
Last MACE ascertainment on or after 180 days of follow-up without experiencing MACE of interest (administrative censoring)	180	1
Discontinue prior to 180 days without experiencing MACE	(date of last MACE assessment – randomization date) + 1	1
Experience non-CV death prior to day 180	(date of death – randomization date)+1	1

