10.4 Analysis of Exploratory Endpoints

The following set of exploratory endpoints is planned in this study. P values are intended to be descriptive. The analysis of the exploratory endpoint will be based on the ITT population.

1. Total number of hospitalizations for coronary, cerebral, or peripheral ischemia from the time of randomization through 30 days
2. Time-to-first occurrence of CV death, MI, or stroke or severe coronary ischemia requiring urgent revascularization from the time of randomization through 90 days
3. Time to first occurrence of CV death, MI, or stroke from the time of randomization through 30 and 60 days
4. Time to first occurrence of MI by type, according to universal definition, from the time of randomization through 90 days
5. Time to occurrence of CV death from the time of randomization through 365 days
6. Time to occurrence of non-CV death from the time of randomization through 365 days

7. Total occurrence of rehospitalization for CV events and all-cause death from the time of randomization through 90 days. Rehospitalization is defined as any site-reported post-index MI hospitalization (including extension of index MI hospitalization past randomization date due to a treatment-emergent serious adverse event) that is adjudicated, regardless of adjudication outcome, or a positively adjudicated triggered event linked to a site-reported adverse event. Urgent heart failure visits with a less than 24 hour stay are not considered.
8. Total occurrence of all-cause death, MI, and stroke from the time of randomization through 90, 180 and 365 days
9. Total occurrence of CV death, MI, and stroke from the time of randomization through 90, 180, and 365 days

10. Medical resource utilization from the time of randomization through 90 days:

- a. Number of total hospitalizations
- b. Length of hospital stay
- c. Number of cardiac care unit (CCU) or intensive care unit (ICU) days
- d. Select surgeries / select procedures related to hospitalization for coronary, cerebral, or peripheral ischemia (see [Section 9.5](#) for definition)
- e. Discharge to: home with additional care, home without additional care, rehabilitation or skilled nursing facilities following hospitalization for coronary, cerebral, or peripheral ischemia

11. Change in EQ-5D-3L data from baseline to day 90

The planned analyses of the exploratory efficacy endpoints are given below in the same order as the list of endpoints above.

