The hospitalizations for coronary, cerebral, or peripheral ischemia through 30 days from the time of randomization, will be analyzed similarly to the key secondary endpoint of hospitalizations through 90 days following randomizations based on a negative binomial regression model.

The exploratory time to event efficacy endpoints listed in 2 through 6 above will be analyzed in a similar manner to that of the primary endpoint. Pre-planned staged PCIs will be excluded in the analysis of the endpoint time to first occurrence of CV death, MI, stroke, or severe

coronary ischemia requiring urgent revascularization. Treatment comparison will be based on a covariate-adjusted Cox regression model for estimating the 1-sided P value, the hazard ratio and its 95% CI. The effect over time will be illustrated with a plot of the complement (1 - KM) of the Kaplan-Meier estimates. Event counts (%) will be presented.

The analysis of the total occurrence of rehospitalization (post-index MI) and all-cause death through 90 days will be based on Win Ratio methodology [Pocock et al, 2012] as described in [Section 10.2.1](#). In this analysis, clinical hierarchy is defined as all-cause death followed by hospitalization. The Win Ratio (CSL112: Placebo) will be calculated along with associated 95% CI and a 1-sided P value. A complete description of the analytical approach is given in [Appendix 15.1](#). Total occurrence of rehospitalization will also be analyzed utilizing a negative binomial model as described previously.

The exploratory endpoints including total occurrence of CV death, MI, and stroke from time of randomization through 90, 180, and 365 days and total occurrence of all-cause death, MI, and stroke from randomization through 90, 180, and 365 days will be analyzed using a negative binomial regression model in a similar manner as described in [Section 10.2.1](#) for the number of hospitalizations through 90 days.

For each exploratory endpoint based on CEC adjudicated outcomes, summary table of consistency of findings between the CEC and investigator-reported MACE will be produced as given in [Section 10.1](#). A supportive listing of individual subject data including the time to event in days and the censoring variable will be presented.

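### The win-ratio P value formula in SAP Appendix 15.1 uses about one quarter of the correct null variance, so z is about doubled

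*SAP*

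**What the plan says.** SAP 10.2.1 adds a supportive analysis to the key secondary endpoint of 90-day ischemic hospitalizations: "A sensitivity analysis of the hospitalization data will be performed to explicitly incorporate death into the outcome using the Win Ratio". The win ratio "will be calculated along with associated 95% CI and a 1-sided P value". SAP 10.4 uses the same method for an exploratory endpoint: "The analysis of the total occurrence of rehospitalization (post-index MI) and all-cause death through 90 days will be based on Win Ratio methodology". Protocol 10.3.2.3.1.1 leaves the method to the SAP ("A complete description of the analytical approach will be provided in the SAP"), and both SAP sections refer to Appendix 15.1 for it.

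Appendix 15.1 compares every CSL112 subject with every placebo subject, so Nt × Nc "paired comparisons are made. Each pair is classified into one of five categories". For the P value it proceeds as follows:

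- U_ij is +1, −1 or 0 for a win, loss or tie, and is defined as: "For each paired comparison ij where Treatment for subject i is not equal to Treatment for subject j".
- U_i is the sum of the U_ij.
- T is the sum of U_i over CSL112 subjects.
- "The variance of T is given by V where" V = [Nt·Nc / (N(N−1))] · ΣU_i².
- z = T/√V is referred to the standard normal distribution for a 1-sided P value.

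The code in SAP Appendix 15.5 contains no win-ratio program.

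**The concern.** The multiplier Nt·Nc / (N(N−1)) belongs to a permutation argument. N fixed scores that sum to zero are dealt at random to two arms, and T is the total dealt to one arm. The argument needs scores that do not depend on the treatment labels, which is true only if U_i is summed over all N−1 other subjects. As printed, U_i is summed over the opposite arm only. It therefore changes with the allocation and is systematically smaller.

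The leading negative binomial analysis otherwise ignores death. The win ratio is there to show whether its result holds once death is included. A z that is twice too large makes weak evidence look strong, whether it favours CSL112 or placebo.

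**Working it through.** **Inputs.** Allocation is 1:1 (SAP 4.1), with 8,700 subjects per group (Protocol 10.1.1). U_i, T, V and z are as printed in Appendix 15.1. The plan gives no power, alpha or expected value for this test, so there is no stated figure to reproduce. The check is whether V equals the null variance of T. The documents give no 90-day death or hospitalization rates for this composite, so the simulation rates below are assumptions.

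**Step 1: T is the same under either scoring.** For two subjects in the CSL112 arm, U_ij = −U_ji, so within-arm comparisons cancel in T. They do not cancel in ΣU_i².

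**Step 2: size of V.** Write k = Nt·Nc / (N(N−1)). Let S be ΣU_i² with all-pairs scores, and let Q be the sum over subjects of the number of other subjects with whom they are not tied. With all-pairs scores, V = k·S. Under the null at 1:1, subject i's opposite arm is a random N/2 of the other N−1 subjects. Sampling without replacement then gives a mean squared opposite-arm score of k·(U_i² + q_i), where q_i is subject i's contribution to Q. Hence

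mean V as printed = k²·(S + Q), and its ratio to the all-pairs V is k·(1 + Q/S).

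At 8,700 per arm, k = 8,700² / (17,400 × 17,399) = 0.250 and Q/S is negligible. The ratio is about 1/4 and z is multiplied by √4 = 2.

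**Step 3: exact small cases, enumerating every allocation.**

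- 3 v 3, six distinct outcomes, 20 allocations. The all-pairs scores are −5, −3, −1, 1, 3, 5, so S = 70, Q = 30 and k = 9/30 = 0.3. True Var(T) = 21.0. All-pairs V = 0.3 × 70 = 21.0. Mean V as printed = 0.09 × 100 = 9.0.
- 6 v 6, with two deaths on different days, four hospitalized survivors (two tied on count) and six event-free subjects, 924 allocations. S = 500, Q = 100 and k = 36/132. True Var(T) = 136.36. All-pairs V = 500 × 36/132 = 136.36. Mean V as printed = (36/132)² × 600 = 44.63, a ratio of 0.33, which falls to 0.25 as N grows.

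**Step 4: null simulation at 8,700 per arm, 3,000 trials per row.** Death day is uniform on 1 to 90 and hospitalization counts are gamma-Poisson with shape 0.5. An earlier death ranks worst, then more hospitalizations. The last two columns are rejection rates at nominal 1-sided 0.025.

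| Assumed deaths / mean hospitalizations | V printed ÷ V all pairs | SD of z as printed | Rejection, as printed | Rejection, all pairs |
|---|---|---|---|---|
| 1% / 0.03 | 0.250 | 1.98 | 16.1% | 1.9% |
| 2% / 0.06 | 0.250 | 1.98 | 15.3% | 2.5% |
| 3% / 0.12 | 0.250 | 1.97 | 15.9% | 2.3% |

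T was identical under the two scorings in every trial. A separate simulation used 4,000 to 8,000 trials per scenario, deaths of 1% to 3% and 0.03 to 0.50 hospitalizations per subject. It gave a variance ratio of 0.250, an SD of z of 1.99 to 2.02, and rejection of 16.0% to 17.0% as printed against 2.3% to 2.6% with all pairs.

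**Step 5: theory and conversion.** With z doubled, the null rejection probability is P(Z > 1.96/2) = P(Z > 0.98) = 0.164.

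- Printed P of 0.025: z = 1.960, halved to 0.980, correct P = 0.164.
- Printed P of 0.005: z = 2.576, halved to 1.288, correct P = 0.099.
- Correct P of 0.10: z = 1.282, doubled to 2.563, printed P = 0.005.

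**The case against.** The best defence is that this is one misplaced restriction in an otherwise sound recipe. The sum defining U_i carries no index limits, V is correct for all-pairs scores, and a published method is cited. A program that scores all pairs would give correct P values, and the documents do not show the program. That is fair as to what will actually be computed. It does not rescue the text: U_ij is defined only for opposite-arm pairs, no other section corrects it, and a programmer or independent validator who follows the appendix would reproduce the error.

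The second objection is about consequence, and most of it stands. The win ratio has no assigned alpha and no decision rule. The gatekeeping in SAP 7.4 covers only H01 to H04, and H02 is a rate ratio estimated from the negative binomial model. For exploratory endpoints SAP 10.4 says "P values are intended to be descriptive". Rehospitalization and all-cause death also have their own models. The 16% rejection rate is therefore conditional on a 0.025 threshold that the plan does not set for this test. Even so, a P value reported only as description has to be computed correctly.

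The third objection is that the missing formula for the promised 95% confidence interval is an omission, not an error. I agree. The interval would be too narrow only if it were built from this z, and the conclusion does not rest on it.

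**Conclusion.** The concern holds against the printed text. At 1:1 allocation and this sample size, V is about one quarter of the null variance of T and z is about doubled. The factor of four is algebraic, and the assumed event rates made no visible difference to it. What is assumed is that the appendix is followed literally.

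The damage is limited to the 1-sided P values of two supportive analyses. The counts Na to Ne and the win ratio Rw = Nw/NL are correct as written. The primary and key secondary tests, multiplicity control and sample size are untouched. It should still be corrected, because the error is large and the sensitivity analysis bears on a formally tested endpoint.

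**What to change.** In Appendix 15.1, define U_ij for every pair i ≠ j in the pooled sample, regardless of arm, and let U_i be the sum over all j ≠ i. Leave T, V and z as they are. Restrict to opposite-arm pairs only when counting Na to Ne and forming Rw.

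Add one sentence stating how the 95% confidence interval for Rw is obtained, either from the corrected z or from a two-sample U-statistic variance. Check that the program matches the corrected text.

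The cost is two sentences and a program check. Data, trial conduct, the point estimate and confirmatory testing do not change.
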